3. TREATMENT OF SUBJECTS

Standard AAA treatment is performed according to current international guidelines. Preparation, preceding this treatment, is adjusted to improve the condition of the patient in the participating centers. Because of the relatively new aspect of training of AAA patients, this will be performed under close observation using a home-monitoring device and the Luscii app.

3.1. Investigational product/treatment

Preoperative questionnaire

In future surgery strategies it is essential to identify patients able to improve their aerobic fitness, by means of a preoperative questionnaire. It has been found that age, frailty, cognitive decline, and disability influence ICU stay in patients over 80 years of age. Of which the clinical frailty scale predicts mortality (21). Patient-reported outcome (PRO) of their own frailty status had more predictive discrimination in surgical patients (22). Whereas physical functioning, instrumental activities of daily living (IADL), and activities of daily living (ADL) are predictive for vascular comorbidities, heart disease and mortality in older Americans with or without diabetes mellitus (DM)(23). Ultimately, the social economic status seems to be of utmost importance in the development of vascular diseases (24).

The following questionnaires are used:

- Age, medical history, medication, smoking, and drinking habits.
- Place of living (postal code).
- Clinical Frailty scale = CSHA CFS (Box 1), frail patients 5 and above.
- Informant questionnaire on cognitive decline in the elderly (IQCODE, 16 questions).
 Cognitive decline ≥ 3,5.
- Ability with the Katz physical, IADL, and ADL score (23):
 - Physical functioning tasks: two mobility tasks (walking several blocks, climbing one flight of stairs) and two strength tasks (lifting 10 pounds, pushing an object).
 - IADL tasks: three cognitive IADLs (using the telephone, managing money, taking medications) and two complex IADLs (grocery shopping, preparing meals)
 - ADL tasks: six personal care tasks (transferring in/out of bed, dressing, bathing, walking across a room, toileting, eating). Defining ≤ 4 as disabling.
- Patient reported outcome (PRO) frailty (25).
- ASA-score.
- Dietary habits, intake of fruits, vegetables, nuts, red meat or fast food. 2-4x a month,
 2-3 x a week, 4-5x a week or daily. Because consumption of fruit, vegetables and nuts 3 times a week is negative associated with aneurysms, whereas consumption of red meat and fast food are positively correlated with abdominal aneurysms (26).

Preoperative exercises

The treatment consists of a daily training at home during weekdays, according to the instructions of a physical therapist, under the supervision of a specialist in sports medicine, and responsibility of the principal investigator. This home training is initiated after heartrate (HR), blood pressure (RR) and oxygenation (SpO2) measurement. Smoking people will be asked to communicate the number of cigarettes smoked each day.

Besides the home training, subjects will be asked to attend a weekly training at the physical therapist. Again, HR, RR and pO2 will be communicated through the home monitoring device.

Before starting the three-to-nine-week training, a cardiopulmonary exercise test (CPET) at the specialist in sports medicine is performed to objectively assess VO₂ at the VAT and other variables related to aerobic fitness. The CPET will be an extra burden to our subjects. After 3-9 weeks of training, this CPET will be repeated to monitor improvement or deterioration of the subjects.

3.2. Use of co-intervention (if applicable)

If unknown cardiologic abnormalities are found during the screening, medication will be adjusted to improve the heart condition of the patient. This is part of the routine workup before an AAA treatment.

3.3. Escape medication (if applicable)

Not applicable

Version number: 4

4. INVESTIGATIONAL PRODUCT

Not applicable, prehabilitation in AAA-surgery will be tested.

5. NON-INVESTIGATIONAL PRODUCT

Not applicable, neither a medicinal, a food product, nor a chemical compound will be investigated.

Version number: 4 20 of 41

6. METHODS

6.1. Study parameters/endpoints

6.1.1. Main study parameter/endpoint

It is aimed to identify AAA patients who improve most from home monitored training, i.e., patients with an improvement of their VO2 at VAT. Patients with poor fitness are expected to benefit most.

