Several trials have established exercise training to be safe in people with AAA and training does not seem to influence aneurysm growth (8-11). Professional supervision (e.g., physical therapy and in-hospital aerobic exercise training) is expensive. Home-based monitoring of exercising patients with AAA is less expensive, and device handling by patients has been positively evaluated before (12).

This study is designed to investigate whether patients with AAA can improve their preoperative aerobic fitness during 3- to 9-week (6 weeks on average) training program. It is primarily designed to evaluate which patients benefit most from this program, based on three outcome measures: initial fitness (CPET), BMI and age. Home training will be performed with home-monitoring and weekly support by a physical therapist.

A successful six-week training program is a true investment, and some patients will not be able to benefit from it. At this point we are unable to select patients who will benefit most. Improvement of aerobic fitness probably depends on a combination of patient specific factors, e.g., age and sex, comorbidity, aerobic fitness at the start of the training, dietary habits, comorbidity, SES, frailty index, ASA-score, physical strength, and the available social support. Training specific factors play a role as well, such as the number of prescribed training sessions, intensity, and the duration. This study is designed to select patients who will benefit most from training, based upon their initial fitness, their BMI and their age. Patients with an AAA and an indication for operative repair were often male smokers, with high blood pressure, and lipid profiles (1). Depending on their diligence, recruitment rate, adherence, completion, drop-out, and attrition rate, will be important. These rates will be evaluated in relation to SES and other characteristics. During training, patients will be supported with dietary substitutes, in order to maintain an anabolic condition (13). Due to the training at home, the Luscii app (CE-certificate 0476) enables patients to ask questions and this might stimulate them to start training, under the suggestion to be observed by the call center.

OBJECTIVES

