Primary Objective: To compare patient characteristics between patients with clear improvement (more than 1.5 ml/kg/min improvement in the VO2 at VAT) after a three-to-nine-week training program, with patient characteristics of those who do not improve after training We aim to identify three factors that predict responsiveness to improve preoperative aerobic fitness following the training program.

Secondary objective: To evaluate the preliminary effectiveness of an, on average, six-week home-monitored training program, in patients with AAA scheduled for elective AAA-repair to improve the preoperative VO2 at the ventilatory anaerobic threshold (VAT).

Other Secondary Objective(s):

Other secondary aims are to evaluate the feasibility of this three-to-nine-week homemonitored training program. A fall-out of some patients is expected because physical exercise requires perseverance and endeavor. This feasibility is evaluated with:

- recruitment rate (how many patients will consent to participate in relation to the patients refusing participation).
- adherence rate (how many patients will endure participation in relation to the patients who give up participation, a.k.a. dropout rate) (Appendix 1).
- completion rate (how many patients will complete participation in relation to the number of patients ending participation).
- drop-out rate (how many patients will drop out of participation in relation to the number of patients completing participation).
- Attrition rate (how many patients will ask if a transfer to another treatment facility is possible, a.k.a. churn rate).

Additionally, the individual (preliminary) effect of prehabilitation on other CPET variables will be evaluated, such as VO₂ at peak exercise (VO_{2peak}) and the oxygen uptake efficiency slope, individual response profiles on the progression in aerobic fitness, improvement of the steep ramp test throughout the program. (Appendix 2).

The postoperative course in patients after AAA repair will be described as well, by collecting data on the surgical intervention and postoperative outcomes (e.g., hospital length of stay (HLOS), number of complications, mortality rate, readmission rate).

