1. STUDY DESIGN

Study design

This is a multicenter single-arm intervention study with a pre- and post-training test, supplemented with enriched nutrient intake. The study will be executed in accordance with the declaration of Helsinki and is registered in ISRCTN registry under reference number 10008907. Written informed consent (IC) will be obtained from all participants.

Participants

Patients >18 years with an indication for AAA-repair will be included in the Treant Hospital (Emmen, Hoogeveen, and Stadskanaal) and in the Wilhelmina Hospital in Assen. This study was designed in close cooperation with the University Medical Center Groningen (UMCG). Patients with an elective indication for operation will be included in this study. Patients will be excluded with an indication for operative intervention within three weeks (semi-elective), patients with connective tissue disorders (e.g., Marfan), patients evaluated unfit for training, and patients unable to understand the meanings of this research.

Recruitment

Consecutive patients with an indication for an aneurysm repair will be asked to participate by their treating physician. The investigator or one of the members of the research team will collect the IC. They will complete a questionnaire with the help of a research nurse and will be assessed for initial eligibility by means of a cardiopulmonary exercise test at the sports medicine office, under the responsibility of the principal investigator (Figure 1). Patients unable to train as indicated by the specialist in sports medicine and/or the cardiologist, will receive necessary medication, and will be excluded. After this judgement, subjects evaluated fit for training, receive the home monitor (pulse oximeter and sphygmomanometer (SMM)) and an explanation how to use the home monitoring app Luscii and FortiFit. The explanation concerning the use of the monitors and FortiFit will be given to the accompanying spouse and/or caregivers, as well. Subjects evaluated unfit for training will receive additional information and follow up by the cardiologist. If, during this follow up, patients medical condition improves, training will be promptly started.

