2.4. Sample size calculation

A multivariable regression analysis will be performed to identify important risk factors, such as a low fitness at the beginning of the training, a low or high BMI ($20 \ge BMI \ge 31$), and a low or high age ($50y \ge age \ge 90y$)(18). With the rule of thumb requiring 10 subjects per variable, and a chance of improvement of 50% (3 variables (fitness t= 0, BMI, and age) x 10 subjects x 0,5= 60); 60 patients will be required to include. Inclusion of one hundred patients will be necessary to perform a multivariable regression analysis with three variables, assuming an exclusion rate of 20%, and a drop-out rate of 20%. Three small sample, randomized controlled trials showed higher VO2 at VAT after 3, 6, or

9 weeks of training in gastroenterological cancer patients, patients with AAA, and rectal cancer patients, respectively: of 10,1%; 18%; or 29% (Table 1)(11, 19, 20).

Version number: 4

Study	Inclusion	n	Wks	% Impro-	VO2	SD	95%CI	VO2	SD	95%CI	ΔVO2
				vement	t=0			t=1			
Berkel(19)	GE-patients	28	3	10,1	9,6	1,2	9,1 - 10,1	10,5	1,36	10 - 11,1	0,9
Barakat(11)	AAA patients	20	6	18	12,2		10,5 - 14,9	14,4		12,3 - 15,4	2,2
Loughney(20)	Rectal CA	17	9	29	11,6	3,4	9,9 - 13,3	15	4,2	12,7 - 17,3	3,4
	total	65			•						

Table 1. Three randomized controlled trials evaluating fitness after training. Wks= weeks, SD= standard deviation, GE= gastroenterological, AAA= abdominal aorta aneurysm, and CA= cancer.

These patients reached an improvement ranging from 0.9 ml/kg/min up to 3.4 ml/kg/min (assumed mean 1.5 ml/kg/min). When subdividing the group of patients into a group with increased fitness (> 1.5 ml/kg/min) and a group without increased fitness (≤ 1.5 ml/kg/min), a dichotomous outcome is reached.

The multivariable analysis will be performed with other patient specific characteristics, as well, such as comorbidities. Modifiable factors will be analyzed as well, such as dietary habits, social economic status, frailty score, and other information collected in the questionnaires.

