Appendix 2; Exercise scheme at home and with the physical therapist

Maandag	Dinsdag	Woensdag	Donderdag	Vrijdag
20 minuten	20 minuten	Fysiotherapeut	20 minuten	20 minuten
wandelen	fietsen		wandelen	fietsen
2 minuten	2 minuten	Steep ramp test	2 minuten	2 minuten
traplopen	traplopen		traplopen	traplopen
1 minuut	1 minuut	HIIT	1 minuut	1 minuut
opstaan-zitten-	opstaan-zitten-		opstaan-zitten-	opstaan-zitten-
opstaan	opstaan		opstaan	opstaan

Table: example of a weekly training program

Thuis (4x per week): vaste tijd (bvb. 9u – 10u) overeengekomen met de fysiotherapeut.
Van tevoren zuurstofsaturatie, pols, RR en aantal sigaretten via de Luscii app
Op basis van CPET:

- 10 / 20 / 30 minuten per dag matig-intensief actief zijn (thuis, mensen merken dat ze meer moet ademhalen):
 - Wandelen
 - o Fietsen
- 1 / 2 / 5 minuten hoog-intensief (thuis):
 - Traplopen
 - o Opstaan uit de stoel en weer gaan zitten.

Na de training wederom O2, pols, RR via de Luscii app doorsturen.

Één keer per week fysiotherapie

[figure not shown]
Van tevoren zuurstofsaturatie, pols, RR en aantal sigaretten via de Luscii app Op basis van aangepaste steep ramp test (10 W /10 s):

Nadat de aangepaste SRT op baseline is uitgevoerd (Figuur 1, Grafieken A en C), kan het (gedeeltelijk) gesuperviseerde trainingsprogramma, bestaande uit 3 HIIT-sessies van 25 minuten per week, worden uitgevoerd in de leefomgeving van de patiënt (in de eerste lijn of thuis).

- Elke trainingssessie bestaat uit een warming-up van 3 minuten op een belasting van 20 W, gevolgd door 14 arbeidsintervallen van 30 seconden op een hoge intensiteit van 60% van de SRT Wpiek
- Afgewisseld met 14 herstelintervallen van 60 sec op een lage intensiteit van 20 W

 Waarna een cooling-down van 1 minuut volgt op een belasting van 20 W (Figuur 1, grafieken B en C).

De trainingsintensiteit tijdens de arbeidsintervallen met hoge intensiteit komt overeen met ongeveer 90% van de CPET Wpiek. De aangepaste SRT dient wekelijks of tweewekelijks herhaalt te worden om veranderingen in de cardiorespiratoire fitheid te monitoren, terwijl het programma dienovereenkomstig kan worden aangepast om een adequate trainingsprikkel te behouden.

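### Initial fitness and the gain in VO2 at VAT share one baseline CPET, so measurement error biases the primary association towards the expected result that poor fitness benefits most

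*Protocol*

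**What the plan says.** - **Design.** Section 1 describes a "multicenter single-arm intervention study with a pre- and post-training test". Section 3.1 has one CPET before training and one repeat after it. No second baseline test and no untrained group are described.
- **Outcome.** The primary objective separates patients with "more than 1.5 ml/kg/min improvement in the VO2 at VAT" from those without. Section 2.4 uses the same cut-off to make the outcome dichotomous.
- **Lead predictor.** The Introduction says the study will evaluate who benefits "based on three outcome measures: initial fitness (CPET), BMI and age". Section 2.4 lists risk factors "such as a low fitness at the beginning of the training" and sizes the study with "3 variables (fitness t= 0, BMI, and age) x 10 subjects x 0,5= 60".
- **Expected direction.** Section 6.1.1: "Patients with poor fitness are expected to benefit most".
- **Analysis.** Section 8.1 compares improved with non-improved patients by multivariable regression.

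The protocol does not say which CPET variable is fitness at t=0. VO2 at VAT is the natural reading, because Table 1 heads its baseline column with VO2 at t=0 and section 3.1 gives VO2 at VAT as the first purpose of the CPET. Nothing in the document mentions test-retest error or regression to the mean.

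**The concern.** The baseline value enters the primary model twice: as a predictor, and with a minus sign inside the outcome. If a patient's first reading is too low, through day-to-day variation or the reading of the threshold, that patient looks unfit at entry and then looks like a responder. A reading that is too high does the reverse. With one baseline test and no comparison group, the data cannot separate this from a real tendency of unfit patients to gain more.

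The direction matters because it matches the one the protocol expects. The Introduction states that the study is meant to identify who benefits most from training. An association inflated by error could make fitter patients look like poor candidates for reasons unrelated to training.

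**Working it through.** **1. The plan's own figure.** Ten improved patients per variable, three variables and a 50% improvement rate give 3 × 10 / 0.5 = 60 evaluable patients. (The printed sum multiplies by 0.5, which would give 15; division is what yields 60.) Adding the two 20% losses gives 60 / (1 − 0.20 − 0.20) = 100. The check therefore uses n = 60.

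**2. Inputs.**
- Mean gain 1.5 and cut-off 1.5 ml/kg/min: section 2.4.
- Significance level 0.05: section 8.2, stated there for the secondary analyses. Two-sided use in the primary model is assumed.
- Observed baseline SD, from Table 1: 1.2 in the 3-week trial and 3.4 in the 9-week trial. The AAA trial gives no SD. Its interval of 10.5 to 14.9 with n = 20, read as a 95% CI, implies (4.4/2)/1.96 × √20 = 5.0. Read as an interquartile range it implies 4.4/1.349 = 3.3.
- Assumed, because the protocol does not give them: error SD 0.5 to 1.3 and SD of true gain 1 to 2 ml/kg/min. At an observed SD of 1.2 the error SD is held to 0.5 to 0.7, since an observed SD already contains the error and 1.3 would exceed it.

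**3. Closed form.** Let pre = T + e1 and post = T + g + e2, with true gain g unrelated to true fitness T. Then change = g + e2 − e1, and its covariance with pre is −s_e². Writing ICC = 1 − s_e²/SD²:
- slope of change on baseline = −s_e²/SD² = −(1 − ICC)
- correlation = −s_e² / (SD × √(s_g² + 2s_e²))

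Both are negative whenever there is any error. Examples:
- SD 3.4, s_e 0.5, s_g 2: −0.25 / (3.4 × √4.5) = −0.03
- SD 3.4, s_e 1.3, s_g 1: −1.69 / (3.4 × √4.38) = −0.24
- SD 1.2, s_e 0.5, s_g 2: −0.25 / (1.2 × √4.5) = −0.10
- SD 1.2, s_e 0.7, s_g 1: −0.49 / (1.2 × √1.98) = −0.29

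**4. Simulation.** Logistic regression of change > 1.5 on baseline VO2 at VAT, BMI and age; 60 patients; no true relation between fitness and gain; at least 4,000 simulated trials per setting.

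| Observed SD | Error SD | Gain SD | ICC | Two-sided false-positive rate | Median OR per SD |
|---|---|---|---|---|---|
| 3.4 | none | 1 | 1.00 | 5% | 1.00 |
| 5.0 | 0.5 | 2 | 0.99 | 5% | 0.96 |
| 5.0 | 1.3 | 1 | 0.93 | 15% | 0.76 |
| 3.4 | 0.5 | 2 | 0.98 | 5% | 0.94 |
| 3.4 | 1.0 | 1 | 0.91 | 17% | 0.74 |
| 3.4 | 1.3 | 1 | 0.85 | 29% | 0.65 |
| 1.2 | 0.5 | 2 | 0.83 | 8% | 0.85 |
| 1.2 | 0.7 | 1 | 0.66 | 41% | 0.59 |

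If 3.4 is taken as the error-free SD, the 29% becomes about 26%. Where the rate is clearly inflated, almost all false positives favour poor fitness.

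**5. Contrast.** When the fitness predictor has error independent of the CPET, at ICC 0.70 to 0.90 and gain SD 1.0, a false result favouring poor fitness occurs in 1.8 to 3.0% of trials (nominal 2.5% in one direction). The median OR is 0.99 to 1.01.

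**6. Offset.** Suppose true gain rises with fitness, at an assumed slope of 1.5/12 = 0.125 with SD 3.4 and gain SD 1.0. The median OR is then 1.04 at ICC 0.90, so the artefact is roughly cancelled, and 1.32 at ICC 0.95, so it is outweighed.

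**The case against.** **The predictor is inferred.** The CPET also yields VO2 at peak exercise and the oxygen uptake efficiency slope, which may share only part of the error in VO2 at VAT. Fitness might also be categorised: in one run at SD 1.2 and error SD 0.7, a median split lowered the false-positive rate from 36% to 24%. This stands as a limit on the size. It does not remove the problem, since any variable from the same test can share its error, and it is a reason to name the variable.

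**The size is assumption-driven.** This stands. A reader might infer that most such trials would falsely confirm the expectation, or that a positive result would have to be an artefact. The documents support neither reading. With small error and a baseline spread as wide as the AAA row allows, the rate is close to nominal, and a real relation in either direction may exist.

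**The steep ramp test could replace the CPET predictor.** A reader might infer this from section 1, which uses the test to estimate aerobic fitness, and from Appendix 2 ("Nadat de aangepaste SRT op baseline is uitgevoerd"). The documents do not carry it that far. Independence of its error is not shown, the baseline test rests mainly on Appendix 2, and the time table in section 6.3 does not list it. It would also change the named predictor. It is suited to a sensitivity analysis.

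**This is a pilot, and corrections belong in a SAP.** The protocol does call the study a pilot, and the expectation in 6.1.1 is a hypothesis and not a decision rule. But the single baseline test, the lack of controls, the change outcome and the choice of predictor are all fixed in the protocol. Modelling follow-up VO2 adjusted for baseline would not help either: that baseline coefficient is the change slope plus 1 and carries the same bias.

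**Conclusion.** The concern holds for the direction of the bias; its size is uncertain. If fitness at t=0 is VO2 at VAT from the baseline CPET, measurement error biases the primary association towards poor fitness predicting improvement, and the design has no means of separating the two. If true gain is unrelated to fitness, the two-sided false-positive rate is about 5% to 29% at an observed baseline SD of 3.4 to 5.0, and about 8% to 41% at SD 1.2, against a nominal 5%. These ranges rest on an assumed error SD (0.5 to 1.3, or 0.5 to 0.7 at the smaller SD), an assumed gain SD of 1 to 2, a continuous predictor and 60 evaluable patients. A true gain that increases with fitness could cancel or reverse the bias. Because the point touches the primary conclusion and costs little to address, it should be dealt with before analysis.

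**What to change.** In sections 2.4 and 8.1:

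1. Name the CPET variable that serves as fitness at t=0.
2. Report its association with response together with a regression-to-the-mean (reliability) correction over a stated range of test-retest error.
3. Add a sensitivity analysis with the baseline steep ramp test of Appendix 2 as the fitness predictor, stating that it helps only if its error is independent of the CPET error.
4. State that an uncorrected association with baseline CPET fitness will not be read as differential benefit or used to select patients.

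The cost is a little more analysis and a more cautious conclusion. The baseline steep ramp test is already described in Appendix 2, though its recording at the first visit should be confirmed. The sample size stays at 60 evaluable and 100 included.
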